#### 8.2 Eligibility visit (cognitive assessment)

##### Healthy volunteer eligibility assessment

Eligibility assessment will take place by discussion with the volunteer and researcher to confirm the inclusion and exclusion criteria, prior to provision of study specific information. Medical records will not be screened to eligibility assess healthy volunteers. Volunteers who meet the inclusion and exclusion criteria will be invited to the cerebral haemodynamics in ageing and stroke medicine (CHiASM) research space for formal consent.

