#### Patient eligibility assessment

Medical records will be reviewed by the direct care team referring the participant for study inclusion, or by LPT/UHL research delivery officers to ensure they meet the inclusion and exclusion criteria prior to referral to the researcher or research delivery team and provision of study specific information. Eligibility screening will only be undertaken by the direct clinical care team for potential participants, or by research delivery officers that are authorised to do so. Members of the research team will only screen medical records to confirm medical and medication history after formal consent to the study has taken place.

In all cases, a permission to screen consent form will be undertaken to allow a Montreal Cognitive Assessment (MoCA) to take place, to ensure deficits are classified as mild to moderate to be eligible for study inclusion. Participants will be counselled that this may preclude them from enrolling in the study, and will be detailed on the permission to screen consent form.

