#### 8.4 Baseline Assessments

Participants who meet the inclusion criteria, will undergo baseline assessments with a member of the research team, or research delivery officer, either at home, designated LPT research space, or invited to attend the CHiASM research space. The first visit will take place at the CHiASM research space, based at the Leicester Royal Infirmary, for an assessment of cognition (ACE-III) and neurovascular function (outline below). Approximately 20-25% of potential participants will have insufficient bilateral temporal windows for assessment, and this would preclude their study entry. Following successful window insonation, and completion of the neurovascular assessment, the following baseline assessments will be undertaken at the same visit or within two weeks at the participant's home: mood (GDS-15), function/ADLs (Lawton-IADL), quality of life (DEMQOL), handedness (Edinburgh handedness inventory).

An assessment of neurovascular function will take place using a protocol validated by this group previously (35). Participants will be asked to refrain from caffeine, nicotine, alcohol, heavy meals, or strenuous exercise for at least four hours prior to the neurovascular assessment. In summary, participants will undergo continuous beat-to-beat monitoring of cerebral blood flow velocity (CBFv) using transcranial Doppler ultrasound (TCD, DWL Doppler box), blood pressure (Finometer), heart rate (3-lead ECG), and end-tidal CO2 (ETCO2, capnography, nasal speculum). Participants will undergo a five-minute baseline recording. Participants will be asked five selected tasks from the ACE-III (attention, memory, language, fluency and visuospatial domains) to stimulate changes in CBFv, which can be measured by the above methods.

For the post-stroke sub-group, a further four tasks will be undertaken. The serial sevens will be completed in addition to serial 2s and 17s, and the naming words with “p” will be completed in addition to words beginning with “r” and “v”. This is to identify subtler deficits that may be present in the stroke sub-group.

Data collected on baseline demographic information will include the following:

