#### 8.5 Randomisation and Codebreaking (if applicable)

Randomisation will be performed using Sealed Envelope®, by the researcher. This is an online-based randomisation tool which uses random permuted blocks to allocate participants to waiting list control or intervention. Participants will be enrolled and assigned a PIN consecutively, and randomised to a treatment arm corresponding to the PIN. Given the nature of the trial, it is not possible to blind participants to the intervention. The Investigator will be providing weekly telephone support with the intervention, in addition to undertaking baseline and follow-up measurements, and therefore blinding of the investigator is also not possible. However, data analysis will be blinded by generating a batch-anonymised data set. Randomisation will be undertaken at the initial visit. As this is an un-blinded trial, code breaking will not be required.

Once participants have been randomised to the intervention arm, they will be provided with information on how to access and use the CT program.

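### Section 8.5 describes no allocation concealment, and three baseline scales may be recorded after the arm is known

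*Combined protocol and SAP*

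**What the plan says.** Section 8.5 is the only account of how allocation works. On who runs it: "Randomisation will be performed using Sealed Envelope®, by the researcher". On the sequence: "This is an online-based randomisation tool which uses random permuted blocks to allocate participants to waiting list control or intervention". On the link between participant and arm: "Participants will be enrolled and assigned a PIN consecutively, and randomised to a treatment arm corresponding to the PIN". It adds that neither participants nor the investigator can be blinded: "The Investigator will be providing weekly telephone support with the intervention, in addition to undertaking baseline and follow-up measurements". The one protection described is a data set anonymised for analysis.

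Eligibility is divided. For healthy volunteers, section 8.2 says: "Eligibility assessment will take place by discussion with the volunteer and researcher to confirm the inclusion and exclusion criteria", with no check of medical records. For patients, the same section says: "Eligibility screening will only be undertaken by the direct clinical care team for potential participants, or by research delivery officers". Section 8.1 sends stroke patients, community-group contacts and self-referrals through clinical, GP or research delivery staff. All populations then meet one more criterion, adequate bilateral TCD windows, which is decided at the first visit under section 8.4: "Approximately 20-25% of potential participants will have insufficient bilateral temporal windows for assessment, and this would preclude their study entry".

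On timing, section 8.5 places randomisation at the initial visit and section 6.1 places it after the first visit. Section 8.4 allows the GDS-15, Lawton-IADL, DEMQOL and handedness assessments either at that visit or at home within the following two weeks.

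**The concern.** There are two routes to bias, and the text closes neither.

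The first is selection at entry. If the person who accepts participants can predict the next arm, acceptance can come to depend on it. In an open trial past allocations are known, and permuted blocks make some future ones predictable. Two entry decisions leave room for judgement: the discussion that settles healthy-volunteer eligibility, and the TCD-window decision, which removes 20-25% of people and may depend on how long the operator persists. Blinding the analysis data set comes too late to correct this.

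The second is measurement of baseline after allocation. The GDS-15, Lawton-IADL and DEMQOL rest on what the participant or an informant reports. If they are completed once both sides know the arm, the baseline is no longer a pre-randomisation value.

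At stake are the arm comparisons in section 11.1 (two-way ANOVA on change from baseline, tested at the 5% level under section 11.3) and the outcome data that are to inform the larger trial's power calculation.

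**Working it through.** **1. Inputs.** From the documents: permuted blocks, two arms, past allocations known to the researcher (8.5); total of 80 (Synopsis) or 60 (11.2). Not in the documents and therefore assumed: 1:1 allocation, one unstratified sequence, and the block size, for which a range is shown. The plan gives no predictability figure to reproduce.

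**2. Predictability with a known fixed block size.** An allocation is certain when one arm has no places left in the block. The best guess otherwise is the arm with more places left; a tie counts as one half.

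- Block of 2 (AB, BA): the second place is always certain, so 1/2 = 50% are certain. Correct guesses: (0.5 + 1)/2 = 75%.
- Block of 4 (six sequences, 24 places): AABB has 2 certain places, ABAB and ABBA have 1 each, and the mirror images double this. Certain: 8/24 = 33%. Correct guesses are 2.5, 3 and 3 for the same three sequences, doubled: 17/24 = 71%.
- Block of 6 (20 sequences, 120 places, enumerated): certain 30/120 = 25%; correct 82/120 = 68%.

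For blocks of 4 the expected number of certain allocations is 80/3 = 26.7 of 80, or 60/3 = 20 of 60. Without blocking, none would be certain and 50% would be guessed.

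**3. Effect of varying the block size.** With sizes mixed at random from 4, 6 and 8, guessing the arm that is behind is still right about 68% of the time (simulation). The gain is that most certain allocations disappear, because the end of a block is no longer known. Varying blocks are therefore not enough alone; the order in which information is released matters more.

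**4. Timing of the baseline scales.**

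| Section | Event | Timing |
|---|---|---|
| 8.4 | TCD-window decision, neurovascular assessment, ACE-III | First visit |
| 8.5 | Randomisation | At the initial visit |
| 6.1 | Randomisation | After the first visit |
| 8.4 | GDS-15, Lawton-IADL, DEMQOL | Same visit or up to two weeks later, at home |

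Under section 8.5, anyone who completes these scales at home does so after allocation. Under section 6.1 the order is undetermined.

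**5. What that does to the analysis.** Change = follow-up − baseline. If knowing the arm moves the recorded baseline by an average of a in the training arm and c in the control arm, the expected arm difference in change moves by −(a − c). Any arm-related shift in baseline passes in full into the quantity analysed. The documents give no basis for a value of a − c, so none is assigned.

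**The case against.** The strongest reply is that this is a gap in reporting, not a demonstrated flaw. Much of that stands.

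A reader might infer that the next allocation can be foreseen. The documents do not show it. A sequence fixed in advance is not a sequence known in advance. The tool is online, the stated order is enrolment, then PIN, then randomisation, and the PIN wording may mean only that the result is filed under that number. Full foreknowledge would need a visible list, and none is described. Partial prediction needs a known or guessable block size, and none is given.

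A reader might also infer that the researcher judges everyone's eligibility. That holds for healthy volunteers only; others screen the records of the patient and stroke groups. Influence elsewhere would run through the TCD-window decision. Section 8.4 allows a research delivery officer to make the baseline assessments, so it is a plausible inference, not a stated fact, that the randomising researcher makes every window decision.

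A third tempting step is to attach a false-positive rate. Suppose people accepted when training is expected are 0.5 SD better than those accepted when control is expected (assumption). Blocks of 4 then shift the arms by 0.5 × (2 × 0.708 − 1) = 0.21 SD. With 40 v 40 the squared standard error is 1/40 + 1/40 = 0.05, and the noncentral F(1,72) gives about 15%. That requires the selection to be on prognosis for change. Section 11.1 analyses change scores, in which a stable difference at entry largely cancels. If selection is instead on the observed baseline score, with an assumed baseline-to-follow-up correlation r of 0.5 to 0.9, the shift is 0.21 × √((1 − r)/2) SD of change, against training, and the rate is 7.5% to 5.5%. The 15% is therefore not a finding about this plan.

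The reply does not dispose of the timing problem. The window decision probably precedes allocation on any reading, but the three later baselines do not have to.

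**Conclusion.** The point holds in this form. Section 8.5 ties the arm to a consecutive PIN in a permuted-block sequence run by an unblinded researcher, and no section describes concealment. With a known fixed block size of 2 to 6, between 50% and 25% of allocations would be certain, and 75% to 68% could be guessed correctly. This assumes 1:1 allocation and one unstratified sequence. How much could in fact be predicted cannot be determined from the documents.

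The timing defect needs no assumption about block size: as written, three of the secondary outcomes can have their baseline recorded after the arm is known.

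The harm falls mainly on the secondary arm comparisons and the data carried into the power calculation. A reader might extend it to recruitment, completion and bilateral CBFv data, but these are feasibility measures and not arm contrasts, and the documents give no mechanism or size for bias in them. The trial should correct this, but it does not undermine the feasibility aim.

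**What to change.** 1. In section 8.5, replace the link between PIN and arm with a statement that the online tool releases the arm only after consent, confirmed eligibility including the TCD-window decision, and entry and locking of all baseline measures. State who holds the sequence.
2. Have the departmental statistician (section 11.6) set randomly varying block sizes, withheld from the researcher. Keep the sizes out of any document the researcher sees.
3. Reconcile the timing of randomisation in sections 6.1, 8.4 and 8.5 so that every baseline measure precedes release of the arm.

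The cost is small: changes to the wording of those three sections and to the set-up of the tool, with no additional assessments. If the tool already withholds the arm in this way, item 1 is mostly a matter of saying so. The real cost is delay. For participants who complete baseline at home, randomisation moves up to two weeks later, and this must fit the limit of four to six weeks from screening in section 8.1 and Appendix C. The alternative is to complete all scales at the first visit, which gives up the flexibility in section 8.4. If anyone has already been randomised under the present text, report what was done and which baselines followed allocation.

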## 6. STUDY DESIGN

### 6.1 Summary of Trial Design

This is a prospective, feasibility, RCT of CT in healthy older adults, and adults with AzD, MCI, or post-ischaemic stroke. This trial is un-blinded, due to the nature of the intervention. The expected duration of participation per individual is three to six months. Initially, participants will be approached by a member of the clinical care team or research support staff, who will screen and identify eligible participants. Study specific information will then be provided by the researcher. Following this, participants will undergo informed consent. Each participant will have two visits (initial and follow-up assessment). After the first visit, participants will be randomised to control or intervention (CT), and will complete an 8-12 week CT program, if selected for the intervention group. Participants will be randomised using Sealed Envelope ©, an online, commercially available randomisation tool. At the end of the trial, participants will be given the option to participate in a qualitative study by semi-structured interviews or focus group. A flow chart for this process can be seen in Appendix A.

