#### 8.6 Subsequent Assessments

Participants randomised to the intervention will be followed-up on a weekly basis by the investigator with a telephone call to troubleshoot any problems arising with software/cognitive training program, or any changes in circumstance that would preclude ongoing study involvement. Participants will be followed up after 8-12 weeks of cognitive training, and will return to the CHIASM laboratory to repeat the baseline assessments (cognition (ACE-III), mood (GDS-15), function/ADLs (Lawton-IADL), quality of life (DEMQOL), neurovascular function (TCD), blood pressure (Finometer), heart rate (3 lead ECG) and end-tidal CO2 (ETCO2, capnography, nasal speculum). Adverse events will also be assessed at this time point.

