## APPENDIX A: PATIENT RECRUITMENT FLOW CHART

**20. APPENDIX B: STUDY FLOWCHART**

## 21. APPENDIX C: SCHEDULE OF PROCEDURES

Procedures	Visits				Windows
	Screening	Baseline	Follow-up	Qualitative arm	
Informed consent	x			x	1 month
Screening MoCA	x				1 month
Demographics	x	x		x (carers)	1 month
Medical history	x	x			1 month
Concomitant medications	x	x			1 month
Eligibility assessment	x				N/A
Randomisation		x			4-6 weeks
Compliance		x	x		N/A
Cognition (ACE-III)		x	x		Baseline: 4-6 weeks, Follow-up: 8-12 weeks from randomisation
Mood (GDS)		x	x		Baseline: 1 month, Follow-up: 8-12 weeks from randomisation
Edinburgh handedness Inventory		x			Baseline: 1 month, Follow-up: 8-12 weeks from randomisation
Function (Lawton-IADL)		x	x		Baseline: 1 month, Follow-up: 8-12 weeks from randomisation
Quality of Life (DEMQOL)		x	x		Baseline: 1 month, Follow-up: 8-12 weeks from randomisation
Neurovascular function (TCD, blood pressure, ECG, ETCO 2 )		x	x		Baseline: 4-6 weeks, Follow-up: 8-12 weeks from randomisation
Adverse event assessments			x		N/A

Telephone Support (intervention arm only)		x	x		Weekly telephone support to participants in intervention arm.
Qualitative interview/focus group (optional)				x	At least 1 week after trial completion

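### Randomisation at the initial visit can come before the home baseline GDS-15, Lawton-IADL and DEMQOL, so these scores may be taken after an unblinded allocation

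*Combined protocol and SAP*

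**What the plan says.** Section 8.5 fixes the time of allocation: "Randomisation will be undertaken at the initial visit". It adds that neither the participants nor the investigator, who takes the baseline and follow-up measurements, can be blinded. On access to the programme it says: "Once participants have been randomised to the intervention arm, they will be provided with information on how to access and use the CT program".

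Section 8.4 places the first visit at the research space, for ACE-III and the neurovascular assessment. Once the neurovascular assessment is complete, "the following baseline assessments will be undertaken at the same visit or within two weeks at the" participant's home. The measures concerned are GDS-15, Lawton-IADL, DEMQOL and the handedness inventory.

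Section 6.1 counts the visits: "Each participant will have two visits (initial and follow-up assessment"). It then gives its own timing for allocation: "After the first visit, participants will be randomised to control or intervention (CT").

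Appendix C marks randomisation, the questionnaires and "Telephone Support (intervention arm only") in the same Baseline column. The window for GDS, Lawton-IADL and DEMQOL reads "Baseline: 1 month, Follow-up: 8-12 weeks from randomisation", without saying what the month is counted from. Section 8.6 times follow-up differently: "Participants will be followed up after 8-12 weeks of cognitive training".

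Section 11.1 (Outcome Data) analyses each participant's baseline-to-follow-up difference by two-way ANOVA. Section 11.7 includes everyone randomised.

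**The concern.** A baseline score used in a between-arm comparison of change should be fixed before anyone knows the arm. Here the home option separates the three questionnaires from the visit at which allocation is made. A home-option participant may therefore rate mood, daily function and quality of life already knowing whether they have training or the waiting list, with an assessor who also knows. In the training arm they may already have begun training.

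Knowledge of the arm can act in both arms; early training acts only in the intervention arm. Either can move the baseline differently by arm, and the change score carries that movement with its sign reversed. Blinding the data analysis, as section 8.5 plans, cannot repair a baseline that has already shifted. Section 11.1 also uses this study's outcome data to size the larger trial, so a distorted difference could carry forward.

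**Working it through.** **Order of events.** The plan gives no figure to reproduce, so the sections are set on one timeline, with the initial visit as day 0.

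| Source | Event | Day |
|---|---|---|
| Section 8.4 | ACE-III and TCD | 0 |
| Section 8.5 | Randomisation | 0 |
| Section 8.5 | CT access information | After randomisation, date not given |
| Section 8.4 | Questionnaires, same-visit option | 0, order against randomisation not stated |
| Section 8.4 | Questionnaires, home option | Up to 14 |
| Section 6.1 | Randomisation, alternative wording | After the first visit, day not given |

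Under sections 8.4 and 8.5 together, home questionnaires come up to 14 days after allocation. Section 6.1 fits randomisation either straight after the first visit or after the home session. Section 8.1 only caps the time from screening to randomisation at four to six weeks. Appendix C sets no order within its Baseline column.

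**Endpoints exposed.** Of the five secondary endpoints in section 6.2, three can be deferred to home (GDS-15, Lawton-IADL, DEMQOL). ACE-III and CBFv cannot. None of the four primary endpoints depends on these scores.

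**Form of the bias.** Suppose a share p of an arm is scored after allocation, this shifts their baseline by d on average, and follow-up scores are otherwise unaffected. That arm's mean change then moves by −p × d. The between-arm difference in change moves by −(p₁d₁ − p₀d₀), where 1 is training and 0 is control. The documents give neither p nor d.

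**Training before baseline.** Section 9.1 sets five sessions a week for 8-12 weeks.
- Full programme: 5 × 8 = 40 to 5 × 12 = 60 sessions.
- Minimum: 0, if training has not started.
- Maximum, assuming an immediate start, full adherence and the full two-week delay: 2 × 5 = 10 sessions; 10/60 = 16.7% to 10/40 = 25%.
- At an assumed 50% adherence: 5 sessions; 5/60 = 8.3% to 5/40 = 12.5%.

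**Questionnaire interval with the full two-week delay.**
- Follow-up counted from randomisation (Appendix C): 8 − 2 = 6 to 12 − 2 = 10 weeks.
- Follow-up counted from training (section 8.6), starting s weeks after randomisation: (8 + s − 2) to (12 + s − 2) weeks. With s = 0 this is 6-10 weeks; with s = 2 it is 8-12 weeks, so nothing is lost.

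A shorter interval could occur in both arms and is not in itself a between-arm bias.

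**The case against.** The best defence is that the order is merely unstated. With only two visits counted, the home session could be read as completing the initial assessment, and Appendix C has no separate home column. Section 6.1 permits randomisation after the home session, and the sequence of sections 8.4, 8.5 and 8.6 suggests baseline first. The Appendix B flow chart, where an order would naturally appear, could not be seen. The consequence is also narrow: it needs the home option, allocation before that session, and a score that moves as a result. The same questionnaires are collected unblinded from everyone at follow-up in any case.

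Much of this limits the point without removing it. Section 8.4 itself contrasts the same visit with the home session, which tells against reading them as one visit. Section 6.1 does not require the questionnaires to be finished first, and section order is not a rule. What stands is that an unseen flow chart might settle the order, that the affected share is unknown, and that unblinded follow-up is a wider exposure which this fix leaves unchanged. The adherence percentage is an assumption and the 10-session figure a ceiling; neither estimates the bias.

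**Conclusion.** The concern holds on the visible text. Followed literally, sections 8.4 and 8.5 put the home-option baselines of GDS-15, Lawton-IADL and DEMQOL after an unblinded allocation, and no visible section prevents it. Three of five secondary endpoints are exposed and none of the four primary ones. The bias cannot be sized without the home-option share and the effect of knowing the arm. Confidence is medium, because the flow charts in Appendices A and B are not visible. The matter should be corrected: the wording change is small, and the scores feed both the between-arm change analysis and the planning of the larger trial.

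**What to change.** Amend sections 6.1 and 8.5 to say: *Randomisation, and release of access to the CT program, take place only after all baseline outcomes (ACE-III, TCD, GDS-15, Lawton-IADL, DEMQOL) are complete; where the questionnaires are done at home, online randomisation follows that session.* Check that the Appendix A and B flow charts agree.

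Two secondary clarifications belong with this:
- State in Appendix C what each baseline window is counted from.
- Reconcile the follow-up timing in section 8.6 with that in Appendix C. Counting from training gives the control arm no starting point.

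For participants already randomised, flag questionnaires dated after randomisation. Keep the all-randomised analysis of section 11.7 as the main one, and add a supplementary sensitivity analysis excluding the flagged scores.

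Randomisation is already online, so no extra visit is needed. The costs are:
- **Delay.** Randomisation comes up to two weeks later for home-option participants. To keep within section 8.1's limit with the full delay, the first visit must fall by week 4 − 2 = 2 (four-week limit) to week 6 − 2 = 4 (six-week limit) after screening.
- **Unequal intervals.** With follow-up counted from randomisation, ACE-III and CBFv baselines could be up to 8 + 2 = 10 to 12 + 2 = 14 weeks before follow-up, against 8-12 weeks for questionnaires done at home just before randomisation. The same rule applies in both arms.
- **A weak sensitivity analysis.** With 20 per group and an assumed 1:1 allocation there are 20/2 = 10 per arm per group. If an assumed 25-50% have flagged home scores, 10 × 0.75 = 7.5 to 10 × 0.50 = 5 remain, or about 5-8. Those remaining may also be selected by frailty or convenience.
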